NCP has a long history of providing program support to local MOVE! teams tasked with delivering MOVE!, and now with implementing **New MOVE!**, through monthly phone calls, quarterly education sessions and *ad hoc* technical assistance. Despite this, local programs often do not align with CPGs; they vary widely in the number of sessions offered and other key characteristics,^{101,149} often because of local organizational barriers.^{100,101,150} Providing more intensive systems redesign and implementation support to help local teams mitigate these barriers will help increase fidelity to **New MOVE!**. Higher fidelity to **New MOVE!** will improve weight outcomes,^{151,152} and a more effective program will help increase Veteran participation and continued engagement. This project will compare an enhanced form of NCP support plus the "Learn. Engage. Act. Program" (LEAP) versus enhanced NCP support alone.

Aim 1: To develop three core products to enhance NCP support to VAMCs and to pilot LEAP in three VAMCs.

H1: Dissemination of products to enhance NCP support will improve MOVE! outcomes.

Aim 2: To determine effectiveness of LEAP plus enhanced NCP support (LEAP+NCP) versus enhanced NCP support alone.

H2: VAMCs with LEAP+NCP will have better MOVE! group outcomes than VAMCs with enhanced NCP support alone.

Aim 3: To conduct formative and cost evaluations to refine design of LEAP and inform future scaling-up of LEAP.

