3.0 Procedures

As described in our Implementation Core*, three core products will be developed in Year 1: 1) a Construct Assessment Tool; 2) a Barrier Busters Tool; and 3) a Program Intelligence Portal (Portal). These products will be made available online for use by MOVE! teams in all VHA facilities. Much of the work has already been done on the Construct Assessment and Barrier Busters Tools. Most of our tool development effort in the first year will be devoted to developing the Portal, which will draw on advanced methods for visually displaying data in a way that has meaning for local teams. For example, users might be interested in seeing geographic displays (e.g., choropleth maps) to visually display where MOVE! participants are coming from compared to non-participants, or longitudinal graphs of engagement and weight outcomes over time. In partnership with OABI, our team will develop a Portal for MOVE! that utilizes next-generation analytic and data visualization tools (e.g., Pyramid Analytics)¹⁵⁶ available through the VA eQuality Measures (eQM) platform. The Portal will be developed using principles of user-centered design that will help to ensure it truly meets the needs of local teams.¹⁵⁷⁻¹⁵⁹ Each of the three products developed in the first year have been specifically chosen to address high-priority gaps. ***In fact, NCP is so eager to embrace these tools we are making them available online to all sites in Year 2*** and will evaluate their effectiveness via interrupted time-series analyses (described below).

Posting products online is likely to achieve only incremental benefits, because local or individual constraints will preclude accessing and using them effectively. Thus, LEAP will be employed to provide intensive support using methods that make it feasible for scaling up to all sites; in fact, we plan to randomize 48 sites (plus three pilot sites) through the course of the project (see Figure 5 below), with the remaining sites acting as controls.

LEAP, as described in the Implementation Core, will be adapted to work with VAMC teams to implement *New MOVE!*. Findings from prior work with a quality collaborative revealed the importance of open communication, relationship building, methods training, monitoring performance, and facilitating team-

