3.1 Study Design

Our goal is to evaluate outcomes for all VAMCs nationwide. For Aim 1, because our NCP partners want to quickly disseminate the core products by posting them online and providing short orientations on national calls, we will use an interrupted time series analysis to assess primary, secondary, and tertiary outcomes before and after dissemination of the products among sites who do not participate in LEAP. Outcome assessments will rely on administrative data available through the Corporate Data Warehouse (CDW). Our team has extensive experience working with MOVE! program data and linking to other utilization and diagnosis data.^{141,142,145-147}

For Aim 2, in years 2-3 we will randomly assign sites to LEAP, six sites at a time. At the beginning of each quarter, sites not included in the pilot and not randomized in previous quarters will be characterized by tertile of performance with respect to aggregate visits (our primary implementation outcome). Two sites will be randomly selected from each tertile of performance to initiate LEAP.

Thus, each cohort of sites will comprise two high performing sites (a key “ingredient” for the LEAP sessions), two “learner sites” and two sites that have moderate performance. This will provide a forum where the more successful sites can “mentor” sites who are further behind. By the end of FY18, 48 sites will have participated in LEAP, plus three pilot sites in FY16. The final three months of follow-up for the last cohort will occur in FY19Q1.

[figure not shown]

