3.2 Key Variables & Analyses

The primary outcome will be VAMC-level aggregated number of MOVE! visits accrued within a six-month analysis period among candidates for MOVE! who live within 40 miles of the VAMC: an implementation outcome with respect to reach.¹⁶⁰ The secondary outcome will be average percentage weight loss by patients at each VAMC at six months after a baseline MOVE! visit. Tertiary outcomes will include: 1) the proportion of patients who have at least 12 MOVE! visits within 12 months (a specified goal in the new CPGs); and 2) the proportion of patients who achieved at least 5% weight loss at six months.

For Aim 1, in addition to developing the three core products, we will evaluate their impact after they are disseminated to VAMCs in FY17 through interrupted time series analyses using administrative program data. Data prior to launch of these products (FY17 Q1) will provide “before” data. “After” data will come from sites not randomized to receive the more intensive intervention (see Aim 2) and up to the randomization time for sites randomized to LEAP. Analytic models will be similar to that of Aim 2, except the primary exposure variable will be an indicator for the period after dissemination of the three core products .

To determine effectiveness of LEAP (Aim 2), we will use a generalized linear mixed-effects model with visit counts and log link for primary outcome, percent weight loss for secondary outcome, and whether at least 12 visits in 12 months were made (1/0) and logit link for tertiary outcomes. Each model will include site as random intercepts and two indicators for tertiles as fixed effects. The primary exposure variable will be the binary time-dependent exposure variable indicating the intervention quarter for the site, i.e., a variable indicating the quarter at or beyond when the site is randomized to initiate LEAP. For each outcome, the

Figure 5: Project Activities and Stepped-wedge Trial Design

Key: Gray = Participation in Learn. Engage. Act. Program (LEAP)

parameter estimate of this exposure variable will allow testing for the effectiveness of LEAP and summarize the LEAP effect expressed as rate ratio for primary outcome, difference in percent weight change for secondary outcome, and odds ratio for tertiary outcome. The model can include other variables (e.g., quarter and participant covariates).

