Power considerations. Across all sites, there will be about 22,080 MOVE! participants (20 participants per closed MOVE! cohort X 1 cohort per quarter X 8 quarters X 147 sites, with 48 sites randomized in steps to LEAP and 99 not randomized). Our previous work showed an average of 4 visits during the 6 months of follow-up and 6% completing at least 8 visits.¹⁴² We assume the minimum detectable and meaningful difference in rates during LEAP in comparison to the control period to be 7 vs. 5 visits (corresponding to a rate ratio of 1.4 and assuming a bit higher rate in control group than the number observed in the preliminary data due to implementation of tools across all sites) and percent of patients with at least 12 visits in 12 months as 10% vs. 7% (corresponding to an odds ratio of 1.48). For power considerations, the design assumes randomization of 6 sites (2 sites per tertile) to LEAP every quarter over 8 quarters starting at Q1 of FY17, and one unexposed quarter, while 3 sites are piloted (Q4 of FY16), no differential effect of LEAP across the tertiles, that 48 sites will be randomized to LEAP (rather than all VAMCs), and a within-site correlation of 0.1. The proposed design will have 99% power to detect the odds ratio of 1.4 or higher and 91% power to detect an odds ratio of 1.48 or higher with a two-sided 0.05 test.

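### The Aim 2 model leaves calendar quarter optional, so with only its committed terms part of any system-wide change would be credited to LEAP

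*Combined protocol and SAP*

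**What the plan says.** Section 3.2 fixes the structure of all Aim 2 models: "Each model will include site as random intercepts and two indicators for tertiles as fixed effects". The exposure is a binary time-dependent indicator, on from the quarter in which a site is randomised to start LEAP. Quarter comes last and is permissive: "The model can include other variables (e.g., quarter and participant covariates". No form is given for it, and no other part of the document commits Aim 2 to a time term.

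Section 3.1 describes the allocation. "At the beginning of each quarter, sites not included in the pilot and not randomized in previous quarters will be characterized by tertile", and then "Two sites will be randomly selected from each tertile of performance to initiate LEAP". Six sites start each quarter for eight quarters, making 48.

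The plan also expects something to change at every site. The core products go online for all sites, with FY17 Q1 as the dividing line for Aim 1 ("Data prior to launch of these products (FY17 Q1) will provide" the before period). Section 1.0 predicts a benefit: "H1: Dissemination of products to enhance NCP support will improve MOVE! outcomes". The power paragraph sets the control rate by "assuming a bit higher rate in control group than the number observed in the preliminary data due to implementation of tools across all sites". Section 3.0 is more cautious: "Posting products online is likely to achieve only incremental benefits, because local or individual constraints will preclude accessing and using them effectively".

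**The concern.** In a stepped-wedge design, quarter is not an ordinary covariate. The number of exposed sites climbs from 0 to 48 as the calendar advances, so exposure and time are correlated by construction. Randomisation makes sites comparable within a quarter and tertile; it does not make early quarters comparable with late ones. A model with site intercepts but no quarter uses both comparisons.

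Aim 2 asks for LEAP plus enhanced NCP support against enhanced NCP support alone. If outcomes rise everywhere, a model without quarter attributes part of that rise to LEAP. If they fall, it hides part of a real benefit. The same model structure serves the primary, secondary and tertiary outcomes.

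Two features look as if they might protect the estimate but do not. The tertile indicators rank sites against one another, so a shift common to all sites leaves them unchanged. The never-randomised sites have an exposure of 0 throughout, so without a quarter term their trend is not used to correct the before-after comparison in the stepped sites.

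**Working it through.** **Inputs from the plan.** Six sites step in per quarter over 8 quarters (48 sites); 147 - 48 = 99 sites are never randomised; the power paragraph has one unexposed quarter, giving 9 quarters. Alpha is 0.05 two-sided.

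**Assumed inputs.** The trends below; log-scale site variance 0.25; site-quarter residual variance 0.06 or 0.15; true rate ratio 1.0. The 25% step is the power paragraph's 4 to 5 visits per participant. That is a historical figure against a planning value, not the VAMC aggregate.

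**The plan's own figure.** For 10% vs 7% with at least 12 visits, the plan states 91% power. A stepped-wedge calculation with 48 sites, 9 quarters, 20 participants per site-quarter, ICC 0.1, variance 0.07 × 0.93 and quarter effects gives SE 0.00898. Power is then Φ(0.03/0.00898 - 1.96) = 91.6%. Without quarter it is 99.9%. This does not identify the model. Over 12 variance conventions, the 48-site calculation with quarter runs from 76.5% to 91.6% and reaches 91% in two. If follow-up is assumed to stop where 12 complete months are no longer available (one unexposed plus six quarters), some settings without quarter give 91.1% to 91.4%.

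**Bias by hand, large site variance.** Take a stepped site with m exposed quarters out of 9.

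- Linear trend: the mean exposed quarter is always 4.5 quarters later than the mean unexposed quarter. The trend runs over 8 quarter steps, so LEAP is credited with 4.5/8 = 0.5625 of the total rise.
- Step at launch: the credited share is Σ(m/9) / Σ(m(9 - m)/9) for m = 1 to 8, which is 4/13.33 = 0.30.

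Spurious rate ratio = exp(share × ln(total change)):

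- 10% rise: exp(0.5625 × 0.0953) = 1.055
- 20% rise: exp(0.5625 × 0.1823) = 1.108
- 10% decline: exp(0.5625 × -0.1054) = 0.942
- 25% step: exp(0.30 × 0.2231) = 1.069

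**Bias by generalised least squares (GLS)** with the assumed variances, both residual values, 147 or 48 sites:

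| Common change | Committed terms only | With categorical quarter |
|---|---|---|
| 10% gradual rise | 1.05 to 1.06 | 1.00 |
| 20% gradual rise | 1.10 to 1.11 | 1.00 |
| 25% step at FY17 Q1 | 1.06 to 1.07 | 1.00 |
| 10% gradual decline | 0.94 to 0.95 | 1.00 |

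Adding the 99 control sites lowers the linear share only from about 0.55-0.56 to 0.52-0.55.

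**Check in a count model.** Poisson random-intercept fits with tertile indicators (400 simulated trials per scenario, about 100 visits per site-quarter, residual variance 0.06) gave, for 147 / 48 sites without quarter: 1.055 / 1.055, 1.108 / 1.110, 1.062 / 1.062 and 0.944 / 0.940, in the order of the table. With quarter the range was 0.996 to 1.003.

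**Effect on the test.** The chance that a null LEAP is declared beneficial is Φ(bias/SE - 1.96). For a 10% gradual rise this runs from Φ(0.0497/0.042 - 1.96) = 22% to Φ(0.0531/0.027 - 1.96) = 50%, against a nominal 2.5%.

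**Sensitivity to the start of data.** If the Aim 2 data begin at FY17 Q1, the launch step lies outside the window and its bias is zero. At the same slope per quarter, the gradual rises still give 1.04-1.05 and 1.08-1.09.

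**The case against.** The strongest defence is that time was not overlooked. Quarter is the first covariate named, and Aim 1 is an interrupted time series whose models are described as similar to Aim 2's. That is fair: the text shows a missing commitment, not a plan to leave time out. A reader might infer that the trial's analysis omitted quarter; the document does not support this. It is a proposal excerpt, and it points to a separate analysis page that was not available for this review.

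The sizes can also be challenged. No trend comes from the plan, Section 3.0 expects only incremental benefit from the tools, and biases of 1.04 to 1.11 are small beside the 1.4 used for power. This stands as a limit on size, but not on direction or mechanism.

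Other adjustments for time can be adequate. That also stands in part, but a linear term relies on the trend being linear, and a step at launch is not.

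Two stronger readings should not be drawn. First, that the 91% power shows quarter was assumed, so that power and model describe different analyses: the power method is not named, and 91% can be reached with or without quarter under different assumptions. Second, that the analysed sites are left open: Section 3.0 says the sites not randomised act as controls, which largely answers this.

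**Conclusion.** The concern holds as a gap in the model statement. Fitted with only its committed terms, the Aim 2 model credits LEAP with roughly half of a gradual system-wide change (52% to 56% in these settings) and about 28% to 30% of a step at launch when one pre-rollout quarter is included. For the assumed trends this means spurious rate ratios of about 1.05 to 1.11 for rises and 0.94 to 0.95 for a 10% decline. These are too small to imitate a rate ratio of 1.4, but large enough to distort a test of a null or modest effect.

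The direction follows from the design. The size rests on assumed trends and variances, and the real system-wide change may have been small. Confidence is moderate, since the linked analysis page may already show quarter in the primary model.

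**What to change.** In Section 3.2, replace the optional wording with a requirement: the primary Aim 2 model for every outcome includes calendar quarter as a categorical fixed effect, alongside the site random intercept, tertile indicators and LEAP indicator. Other covariates can stay optional. Because the study has been conducted, the practical step is to confirm that quarter was in the primary model, or to re-run with it if it was not. The first quarter of Aim 2 data should be stated at the same time.

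No new data are needed, as outcomes come from administrative records. The cost is precision. With the remaining sites as controls, the LEAP standard error grows by about 10% (0.027 to 0.030 at residual variance 0.06; 0.042 to 0.046 at 0.15). With only the 48 stepped sites it grows by about 50% (0.027 to 0.041; 0.043 to 0.064). Even at 0.064, power for a rate ratio of 1.4 is Φ(0.3365/0.064 - 1.96) = Φ(3.30), above 99%. For the 12-visit outcome with one unexposed quarter, power with quarter is 96% or more with 147 sites, and 76.5% to 91.6% with 48.

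### Aim 2 counts one unexposed quarter, shorter than its six-month outcome window, and leaves quarter effects optional; a stated longer baseline with mandatory quarter effects would be a cheap improvement

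*Combined protocol and SAP*

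**What the plan says.** Section 3.2, Power considerations, assumes that six sites, two from each tertile, enter LEAP at each of eight quarterly steps, "starting at Q1 of FY17, and one unexposed quarter". The unexposed quarter is FY16 Q4, when the three pilot sites run. Of the 147 other sites, "48 sites randomized in steps to LEAP and 99 not randomized".

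The primary outcome in Section 3.2 is a site-level count of visits over a six-month analysis period. A tertiary outcome needs 12 months of follow-up. The Aim 2 model has a site random intercept, two tertile indicators and a time-dependent LEAP indicator. Quarter is named only as a variable that the model may include. The number of pre-LEAP quarters to be analysed is not given.

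On data, Section 3.1 states: "Outcome assessments will rely on administrative data available through the Corporate Data Warehouse (CDW"). For Aim 1, Section 3.2 states: "Data prior to launch of these products (FY17 Q1) will provide" the before-period. That section keeps LEAP sites in Aim 1 until they are randomized, whereas Section 3.1 describes Aim 1 as covering sites that do not take part in LEAP. Section 3.1 also ranks all eligible sites by aggregate visits before each randomization, so some earlier visit data are needed for every site before the first step.

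**The concern.** The first cohort has a single control quarter, while the outcome takes two quarters to accrue. Unless the plan says how windows line up with quarters, the first cohort may have no fully unexposed value of the primary outcome.

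The unexposed quarter also differs in kind from later control time. Aim 2 compares LEAP plus enhanced support with enhanced support alone (Section 1.0), and the core products that make the support enhanced launch in FY17 Q1. A model without quarter effects credits part of the change from the pre-product to the product period to LEAP. Adding earlier quarters without quarter effects would make this worse. With quarter effects, the earlier quarters can sharpen each site's own baseline at little cost.

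**Working it through.** **Outcome window.** Section 3.2 does not say how six-month periods map to quarters.
- Forward from FY16 Q4: the window covers FY16 Q4 and FY17 Q1. The first cohort starts LEAP in FY17 Q1, so half of its window is exposed. A 12-month window from FY16 Q4 runs to FY17 Q3 and crosses the start of the first three cohorts.
- Backward from FY16 Q4: the window is unexposed, but it already uses FY16 Q3, so more than one quarter of data is needed.
- With FY16 Q1-Q3 added: forward six-month windows opening in FY16 Q1, Q2 and Q3 all close before LEAP, as does a 12-month window opening in FY16 Q1.

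**Reproducing the stated 91%.** Inputs from Section 3.2: 48 sites in 8 steps of 6; one baseline quarter, so T = 9 periods; m = 20 per site-quarter ("20 participants per closed MOVE! cohort X 1 cohort per quarter X 8 quarters X 147 sites"); "a within-site correlation of 0.1"; 10% v 7%; "with a two-sided 0.05 test". Assumptions: total variance p0(1 − p0) = 0.07 × 0.93 = 0.0651, and fixed quarter effects.
- τ² = 0.1 × 0.0651 = 0.00651; σc² = 0.9 × 0.0651 / 20 = 0.0029295.
- Exposed site-quarters U = 6 × 36 = 216. W = 36 × 204 = 7,344 (squared column totals). V = 6 × 204 = 1,224 (squared row totals).
- Hussey-Hughes: Var = I σc² (σc² + Tτ²) / {(IU − W)σc² + (U² + ITU − TW − IV)τ²}.
- T = 9: numerator 48 × 0.0029295 × 0.0615195 = 0.008651; denominator 3,024 × 0.0029295 + 15,120 × 0.00651 = 107.29. Var = 0.00008063, SE = 0.00898, power = Φ(0.03/0.00898 − 1.96) = 91.6%.

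This agrees with the stated 91%. Other 48-site variance choices with quarter effects give about 77% to 89%. Dropping quarter effects or adding the never-randomized sites gives 96% or more.

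**Longer baseline, same model.** With four baseline quarters T = 12, and U, W and V are unchanged. Numerator 48 × 0.0029295 × 0.0810495 = 0.011397; denominator 3,024 × 0.0029295 + 24,192 × 0.00651 = 166.35. Var = 0.00006851, a ratio of 0.850; SE = 0.00828 (−8%); power 95.2%. Two baseline quarters give 93.3% and eight give 96.9%.

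**If site correlation is not constant** (my assumption; the plan gives no decay). Let the covariance between quarters j and k be τ²d^|j−k|. For a correctly specified model, Var is the LEAP element of (ΣX'Ω⁻¹X)⁻¹. For a random-intercept model V0 fitted to such data, the true variance is the LEAP element of A⁻¹(ΣX'V0⁻¹ΩV0⁻¹X)A⁻¹ with A = ΣX'V0⁻¹X. The 48-site results, four baseline quarters v one, are:

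| Decay per quarter | Variance ratio, correct model | Variance ratio, random intercept only | True / model-based variance, 1 → 4 quarters |
|---|---|---|---|
| 5% | 0.949 | 1.040 | 1.49 → 1.83 |
| 10% | 0.973 | 1.100 | 1.92 → 2.49 |
| 20% | 0.990 | 1.110 | 2.60 → 3.39 |

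**Bias if quarter is omitted.** Take 4 visits in all pre-FY17 quarters, 5 afterwards, and no LEAP effect. Let δ = ln(4/5) = −0.2231, B = number of pre-product quarters, T = B + 8, and φ = τ²/(σc² + Tτ²). Random-intercept least squares on the log scale gives

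ln RR = (−BδU/T) / {U − φV − U²(1 − φT)/(IT)}.
- B = 1: φ = 0.1/(0.045 + 0.9) = 0.1058; 5.355 / (216 − 129.52 − 5.14) = 0.0658; RR = 1.07.
- B = 4: φ = 0.1/(0.045 + 1.2) = 0.0803; 16.066 / (216 − 98.31 − 2.93) = 0.1400; RR = 1.15.

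Adding the 99 other sites hardly changes this (1.065 and 1.148). With quarter fixed effects the estimate is 1.00 in each case.

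**The case against.** The strongest case on the other side is that no error is shown. The single quarter is a power assumption. Later cohorts have up to eight control quarters, the 48 sites split evenly into 216 unexposed and 216 exposed site-quarters, and the stated powers are already 99% and 91%. Pre-product quarters lack the comparator condition, and Section 3.0 expects sites to differ in how well they use the products, so common quarter effects remove only the average shift. Leaving out older quarters is therefore defensible. All of this stands. It limits the point to an improvement and is why a sensitivity analysis belongs in the fix.

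Four stronger readings are tempting but not supported:
- A reader might infer that the analysis is confined to one quarter. Section 3.2 imposes no such limit; it is silent. Figure 5, which was not available for this check, may show more.
- A reader might infer that earlier data are already extracted. The Aim 1 text is prospective, gives no number of quarters, and conflicts with Section 3.1 on whether LEAP sites are included.
- A reader might take the added quarters as free precision. They are not free without quarter effects, and the random-intercept model as written can lose precision if the correlation decays.
- A reader might quote a 25% variance reduction, from the 147-site calculation (ratio 0.752). That calculation also relies on constant correlation, and with those sites one baseline quarter already gives 99.6% power for 10% v 7%. The 48-site variant is the one that reproduces the plan's figure.

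**Conclusion.** The point holds as a low-cost improvement and does not show an error in the stated power. Two parts do not depend on the precision calculation. The plan should say how a six-month window fits a one-quarter baseline for the first cohort. Quarter effects should not be optional, because even the single planned quarter predates the core products.

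The bias figures of 1.07 and 1.15 assume that the historical 4 visits apply to all pre-FY17 quarters and that the rise to 5 is immediate; a smaller or slower rise would give less. The precision gain (variance −15%, SE −8%, power 91.6% to 95.2%) assumes constant site correlation and applies to the 10% v 7% outcome. Under 5-20% decay per quarter it shrinks to about 1-5% of variance with a correct model, or becomes a loss of about 4-11% with a random intercept alone. For the primary count no dispersion is given, so its precision gain cannot be quantified; its stated power is already 99%.

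**What to change.** 1. Prespecify fixed quarter effects in every Aim 2 model.
2. State how the six- and 12-month windows map to quarters and to the LEAP indicator, and how a window that straddles a site's LEAP start is coded.
3. Include FY16 Q1-Q3 with FY16 Q4 as unexposed periods for the 147 non-pilot sites, so that the first cohort has complete six-month windows before LEAP.
4. Allow site correlation to change over time, for example by decaying correlation or site-by-quarter effects, with robust standard errors.
5. Report a sensitivity analysis without the added quarters.
6. Reconcile Sections 3.1 and 3.2 on whether LEAP sites contribute to Aim 1, and align the power paragraph with the chosen baseline.

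The cost is a longer administrative extract, a slightly more complex model and some reliance on pre-product quarters. No further sites or participants need to be recruited.

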2.1 LEAP

Quality collaboratives are often successful in helping local implementation teams identify and address barriers through systems redesign approaches. For example, the Stroke QUERI-led evaluation of a quality collaborative resulted in significant improvements in stroke care by improving fidelity of the care provided with CPGs.^{92,93} However, the challenge with traditional collaboratives is that they are relatively resource-intensive, e.g., travel and time off for week-long kick-off meetings, site visits by expert facilitators, etc.⁹⁴ It is often infeasible to scale these resource-intensive programs within VHA with 150 VAMCs and 819 outlying clinics.

We have designed LEAP to overcome these issues by leveraging best practices in distance-learning, which has long wrestled with how to effectively engage participants in learning and hands-on program activities.⁹⁵ LEAP was conceived to provide intensive support using methods that make it feasible for scaling up to involve many sites. It is a multi-faceted implementation strategy that will involve an intensive distance learning series of workshops designed to engage local teams. LEAP will draw on the best of quality collaboratives^{92,96} and meld these components with distance learning technologies to create a scalable yet intensive support system. LEAP will help teams navigate their local settings and mitigate barriers to implementing new initiatives (i.e., New MOVE! and shared decision making for lung cancer screening in projects 1 and 2) by building skills in open communication, developing productive working relationships, providing methods training and program monitoring, and building team-based problem-solving skills.

Table 1: LEAP Program Components & Strategies

Sessions	CFIR Construct Addressed ⁷⁵	Discrete Strategies & Tools
Pre- and overall	Planning Engaging	Capture and share local knowledge ⁹¹ TAMMCS: SIPOC Mapping Create a learning collaborative ⁹¹ Make training dynamic ⁹¹ Recruit, designate, and train for leadership ⁹¹ TAMMCS: Charter ⁹⁷ Provide ongoing consultation ⁹¹
1-5	Planning Engaging Self-efficacy	System Redesign (SR) improvement model ⁹⁷ Develop a formal implementation blueprint ⁹¹ TAMMCS: SMART Aims, Charter ⁹⁷ Assess for readiness; identify barriers and facilitators ⁹¹ Context Assessment Tool Audit and provide feedback ⁹¹ Program Intelligence Portal Promote adaptability ⁹¹ Tailor strategies ⁹¹ Barrier Busters Tool Promote network weaving ⁹¹

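### The power paragraph misstates two of its own figures: the participant total is not its printed product (22,080 against 23,520), and the rate ratio of 1.4 is called an odds ratio

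*Combined protocol and SAP*

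**What the plan says.** All the size and power figures stand in the power considerations paragraph of section 3.2 (Key Variables & Analyses) of the combined protocol and SAP.

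- **Participants.** "Across all sites, there will be about 22,080 MOVE! participants (20 participants per closed MOVE! cohort X 1 cohort per quarter X 8 quarters", multiplied by 147 sites. The paragraph splits the 147 into 48 sites randomized in steps and 99 not randomized.
- **Effect on visits.** The target is "7 vs. 5 visits (corresponding to a rate ratio of 1.4"). The control value of 5 is set a little above earlier experience, "an average of 4 visits during the 6 months of follow-up".
- **Effect on the 12-visit outcome.** 10% against 7% of patients with at least 12 visits in 12 months, given as an odds ratio of 1.48.
- **Design assumptions.** Six sites start LEAP each quarter over 8 quarters, with one unexposed quarter. The list ends "that 48 sites will be randomized to LEAP (rather than all VAMCs), and a within-site correlation of 0.1".
- **Power.** "99% power to detect the odds ratio of 1.4 or higher and 91% power to detect an odds ratio of 1.48 or higher", two-sided 0.05.

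Earlier in section 3.2 the primary outcome is defined as each VAMC's total of MOVE! visits over six months, and the effect measures are fixed: "LEAP effect expressed as rate ratio for primary outcome, difference in percent weight change for secondary outcome, and odds ratio for tertiary outcome". Section 3.0 has 48 sites randomized "with the remaining sites acting as controls". Section 2.1 (LEAP) describes the setting as "within VHA with 150 VAMCs and 819 outlying clinics".

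**The concern.** Two statements in the paragraph conflict with figures printed beside them. The total is given with all its factors, and they do not multiply to it. The closing sentence applies one label, odds ratio, to two effects that the paragraph has just defined on different scales for different outcomes. As printed, the smaller odds ratio carries the higher power (99% at 1.4, 91% at 1.48), which cannot be true of any single outcome.

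What is at stake is the record of how the trial was sized. The 99% is the only power figure that can belong to the primary outcome, yet the sentence names no outcome and gives the wrong effect measure. A reader trying to reproduce it also lacks two inputs: the set of sites used, and the variability assumed for visit counts.

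**Working it through.** **1. Participant total.** Inputs, all from the power paragraph: 20 per cohort, 1 cohort per quarter, 8 quarters, 147 sites.

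- 20 x 1 x 8 x 147 = 23,520; stated 22,080.
- Difference: 23,520 - 22,080 = 1,440, and 1,440 / 23,520 = 6.1%.
- Solving for one factor at a time: 22,080 / (20 x 8) = 138 sites exactly; 22,080 / (8 x 147) = 18.8 participants; 22,080 / (20 x 147) = 7.5 quarters. Only the site count gives a whole number.
- The 147 agrees with the rest of the document: 48 + 99 = 147, and 150 VAMCs less 3 pilot sites = 147.

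**2. Effect sizes.**

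- 7 / 5 = 1.40, a rate ratio, as the paragraph says.
- (0.10 / 0.90) / (0.07 / 0.93) = 1.476, an odds ratio, as the paragraph says.

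Both values are right. Only the label on 1.4 in the last sentence is wrong.

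**3. What a literal odds ratio of 1.4 would give.** On the 7% base the odds are 1.4 x 0.07 / 0.93 = 0.1054, so the LEAP proportion is 0.1054 / 1.1054 = 9.53% and the difference is 0.0253.

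I used the Hussey-Hughes variance with quarter effects, 9 quarters (T), 20 per site-quarter and within-site correlation 0.1. With v = p(1 - p), let s = 0.9v / 20 and t = 0.1v. For I sites,

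Var = I s (s + T t) / [(I U - W) s + (U^2 + I T U - T W - I V) t].

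Six sites step in at each of 8 quarters, so U = 6 x 36 = 216, W = 36 x 204 = 7,344 and V = 6 x 204 = 1,224. With v at the control rate, v = 0.0651, s = 0.00293 and t = 0.00651.

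- 48 sites: Var = 0.008651 / (3,024 s + 15,120 t) = 0.008651 / 107.29, so SE = 0.00898.
- 147 sites: Var = 0.026493 / (24,408 s + 86,400 t) = 0.026493 / 633.97, so SE = 0.00646.

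Power is the normal probability below difference / SE - 1.96. The plan's 10% v 7% comes first, then the literal reading. The three values take v at the control, mean and LEAP rate.

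| Effect | 48 sites | 147 sites |
|---|---|---|
| 10% v 7% (odds ratio 1.48) | 91.6 / 86.4 / 81.1% | 99.6 / 98.9 / 97.7% |
| 9.53% v 7% (odds ratio 1.4) | 80.5 / 74.3 / 68.8% | 97.5 / 95.3 / 92.6% |

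The limits shift with convention. With 8 quarters instead of 9, the second row becomes 65-77% and 88-95%. Without quarter effects it rises to 96-99% for either site set, but 10% v 7% then rises to 99% or more. Under every convention 1.4 has less power than 1.48, so the printed pair cannot describe one outcome.

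**4. Effect of the total on power.** For 10% v 7%, 138 sites give 99.6 / 98.8 / 97.5% against 99.6 / 98.9 / 97.7% with 147: at most 0.2 points.

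**5. Is 99% credible as a rate ratio for the primary outcome?** The documents give no dispersion for visit counts or site totals, so these inputs are assumptions: log scale, effect ln(1.4) = 0.336, between-site log variance 0.1-1.0, six-month residual log variance 0.1 or 0.2, five non-overlapping half-years with period effects, and half exposure for a site that starts mid-window.

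- All 147 sites: above 99.9% (residual 0.1); 99.2-99.9% (residual 0.2).
- 48 sites alone: 98-99% (residual 0.1); 81-88% (residual 0.2).
- 48 sites, residual 0.2, no period effects: 99.8-99.9%.

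**The case against.** The strongest reply is that both errors are slips whose meaning can be recovered. The paragraph defines 1.4 as a rate ratio shortly before mislabelling it, section 3.2 assigns each effect measure to its outcome, and the total hardly enters the power. The opening statement also says that the trial has been conducted and that the text is an excerpt from the funding proposal. All of this stands, and it limits the weight of the point. It does not make the printed figures right. Nor does the word about excuse the total, because the exact factors are printed with it.

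A reader might go further and infer that the 99% fails for the primary outcome, since it appears to rest on visits per participant while the outcome is a site total. The documents do not support that. Per participant is itself an inference from the earlier average of 4 visits. With participant numbers held fixed, as the paragraph holds them, a ratio of 1.4 per participant is also 1.4 in the total. The low result in step 5 (81-88%) needs the 48 sites alone, the larger assumed residual, non-overlapping half-years, half-coded exposure where the plan has a binary one, and period effects that section 3.2 leaves optional.

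Nor does the 91% prove a 48-site calculation. It matches one variance convention with 48 sites, but 91.8% also arises with 147 sites if 8 periods and a decaying within-site correlation (autocorrelation 0.8) are assumed.

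**Conclusion.** Two errors are certain and rest on the document's own numbers: the total is 1,440 (6.1%) below its printed product, and 1.4 is a rate ratio labelled as an odds ratio. The literal-reading power of roughly 69-81% (48 sites) or 93-97% (147 sites) depends on quarter effects and the variance convention; the labelling error does not.

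Beyond these there is a reporting gap. The paragraph does not say which sites each power figure uses, and its only variance input is a within-site correlation of 0.1, although the primary outcome is a six-month VAMC total. This is not evidence that the 99% is wrong or that the trial is underpowered. With all 147 sites, which is how section 3.0 describes the comparison, 99% is plausible over the assumed range.

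**What to change.** - Reconcile the total with the site count: 23,520 for 147 sites, or a corrected site count if 138 was meant. Only the sponsor can say which.
- Restate the closing sentence as 99% power for a rate ratio of 1.4 in visits, and 91% power for an odds ratio of 1.48 for at least 12 visits in 12 months (tertiary outcome).
- For each figure, say whether it uses the 48 randomized sites or all 147. Give the dispersion assumed for visit counts and the unit it refers to, participant or VAMC total.

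The cost is a few sentences, plus retrieving the inputs of the calculation already made. The design, analysis model and test do not change. As the trial has been conducted, this corrects the record of the plan.
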